12.7. Appendix 7: Classification of Heart Failure

Physicians usually classify patients' heart failure according to the severity of their symptoms [[American Heart Association, 2014](#)]. The table below describes the most commonly used classification system, the NYHA Functional Classification. It places patients in one of four categories based on how much they are limited during physical activity.

Class	Functional Capacity: How a patient with cardiac disease feels during physical activity
I	Patients with cardiac disease but resulting in no limitation of physical activity. Ordinary physical activity does not cause undue fatigue, palpitation, dyspnea or anginal pain.
II	Patients with cardiac disease resulting in slight limitation of physical activity. They are comfortable at rest. Ordinary physical activity results in fatigue, palpitation, dyspnea or anginal pain.
III	Patients with cardiac disease resulting in marked limitation of physical activity. They are comfortable at rest. Less than ordinary activity causes fatigue, palpitation, dyspnea or anginal pain.
IV	Patients with cardiac disease resulting in inability to carry on any physical activity without discomfort. Symptoms of heart failure or the anginal syndrome may be present even at rest.

Class	Objective assessment
A	No objective evidence of cardiovascular disease. No symptoms and no limitation in ordinary physical activity.
B	Objective evidence of minimal cardiovascular disease. Mild symptoms and slight limitation during ordinary activity. Comfortable at rest.
C	Objective evidence of moderately severe cardiovascular disease. Marked limitation in activity due to symptoms, even during less-than-ordinary activity. Comfortable only at rest.
D	Objective evidence of severe cardiovascular disease. Severe limitations. Experiences symptoms even while at rest.

For Example:

- A patient with minimal or no symptoms but a large pressure gradient across the aortic valve or severe obstruction of the left main coronary artery is classified: Function Capacity I, Objective Assessment D.
- A patient with severe anginal syndrome but angiographically normal coronary arteries is classified: Functional Capacity IV, Objective Assessment A.

12.8. Appendix 8: Country Specific Requirements

No country-specific requirements exist.

**Description:**

- The purpose of this RAP is to describe the planned efficacy and safety analyses and output to be included in the Clinical Study Report for Protocol 200622.
- This RAP defines the content of the headline results and SAC deliverables.

## 1. INTRODUCTION

The purpose of this reporting and analysis plan (RAP) is to describe the analyses to be included in the Clinical Study Report for Protocol 200622:

Protocol Revision Chronology:		
2013N171550_00	29-APR-2016	Original

### 1.1. RAP Amendments

Revision chronology:

RAP Section	Amendment Details
Reporting and Analysis Plan_200622_Final_V1 [12-FEB-2019]	
Reporting and Analysis Plan_200622_Amendment_Final_V1 [18-JUN-2019]	
Section 5.2	
 
Update to the definition of baseline ECG to include ECG findings
 

Section 5.4.1.1	
 
Update to the OCS conversion table to include fluticasone
 

Section 6.1	
 
Additional details for the summary of steroid perception questionnaire
 

Section 7.1.4.1	
 
Specify an additional sensitivity analysis of the primary estimand excluding subjects from a single site in Mexico.
 

Section 7.4.4.1	
 
Update to the sensitivity analysis for missing data for the rate of HES flares endpoint
 

Section 7.5.4	
 
Clarification of the implementation of the Wilcoxon rank sum test
 

Section 7.6.8	
 
Update to the derivation of MSAS-SF endpoints to include detail of conversion of categorical responses to numeric scores.
 

Section 14	
 
New section for exploratory exposure-efficacy response analysis
 

Section 16.4	
 
Define treatment phases for HES flare and other efficacy assessments
 

Section 16.6	
 
Define derivation of total observed time, time on treatment, time off treatment, missing time (days)
 
Clarification of QTcB calculation
 

Section 16.8	
 
Additional PCI range for Creatine Phosphokinase
 

Section 16.10	
 
Updates to relevant display titles in line with changes above
 
Minor changes to titles of summary tables for AESIs
 

## 2. SUMMARY OF KEY PROTOCOL INFORMATION

### 2.1. Study Objective(s) and Endpoint(s)

Objectives	Endpoints
Primary Objectives	Primary Endpoints

 
To demonstrate the efficacy of mepolizumab compared with placebo based on maintenance of control of HES symptoms during the treatment period.
 
	
 
Proportion of subjects who experience a HES flare during the 32-week study treatment period
 

Secondary Objectives	Secondary Endpoints

 
To demonstrate supportive evidence of the benefit of mepolizumab compared with placebo based on other measures of efficacy.
 
	
 
Time to first HES flare
 
Proportion of subjects who experience a HES flare during Week 20 through Week 32
 
Rate of HES flares
 
Change from baseline in fatigue severity based on Brief Fatigue Inventory (BFI) item 3 (worst level of fatigue during past 24 hours) at Week 32
 

Exploratory Objectives	Exploratory Endpoints

 
To investigate mepolizumab compared with placebo with respect to additional measures of efficacy.
 
	
 
Proportion of subjects who have an elevated blood eosinophil level that meets the pre-defined threshold during the 32-week study treatment period
 
Lung function tests (FEV1, FVC, and ratio)
 
Echocardiogram
 


 
To investigate the efficacy of mepolizumab compared with placebo with respect to patient and clinician reported symptoms, health status, and disease impact.
 
	
 
Change from baseline in HES symptom severity based on HES Daily Symptoms (HES-DS) at Week 32
 
Change from baseline in the BFI total score at Week 32
 
Clinician- and subject-rated overall response to therapy score (RTS) at Week 32
 
Change from baseline in Subject-rated symptom severity (SSR) at Week 32
 
Change from baseline in Modified Memorial Symptom Assessment Scale-Short Form (MSAS-SF) responses at Week 32
 
Change from baseline in physical function (Patient Reported Outcome Measurement Information System [PROMIS] physical function items) at Week 32
 
Change from baseline in sleep (PROMIS sleep items) at Week 32
 

Objectives	Endpoints

 
To characterize the patient burden of HES.
 
	
 
SF-36 v2
 
Healthcare resource utilization (HCRU)
 
Work Productivity and Activity Impairment Index – General Health (WPAI-GH) v2
 
Steroid perception questionnaire
 

 
To investigate the pharmacokinetics (PK) of mepolizumab.
 
	
 
Plasma concentration of mepolizumab
 

 
To investigate the pharmacodynamics (PD) of mepolizumab.
 
	
 
Total IL-5
 
Blood eosinophil levels
 

Safety Objectives	Safety Endpoints

 
To evaluate the safety of mepolizumab compared with placebo in subjects with HES receiving standard of care treatment over a 32-week study treatment period.
 
	
 
Adverse events including local injection site reactions and systemic reactions (e.g., hypersensitivity)
 
Vital signs
 
12-lead ECG
 
Hematological and clinical laboratory tests
 
Immunogenicity (anti-drug antibody)
 

Protocol endpoint was the proportion of subjects who receive blinded active oral corticosteroid (OCS) due to an elevated blood eosinophil level that meets the pre-defined threshold (2 x baseline value or baseline value + 2500 cells/ $\mu$ L) during the 32-week study treatment period. See Section 2.4 for rationale for change.

Protocol endpoint was change from baseline in the BFI total and domain scores at Week 32. See Section 2.4 for rationale for change.

Protocol endpoint was the proportion of subjects with a favourable response as measured by clinician- and subject-rated overall response to therapy score (RTS) at Week 32. See Section 2.4 for rationale for change.

Serum free and total IL-5 were planned in the protocol. See Section 2.4 for rationale for change.

## 2.2. Study Design

Overview of Study Design and Key Features	

             ↑ Treatment              (R) Randomization              ★ Blood eosinophil count measure (~2 weeks after randomization)              # Subjects who continue with open-label mepolizumab will have the last assessment on Week 32 prior to receiving open-label mepolizumab.              A For subjects who do not continue with open-label mepolizumab after completing Visit 11 assessment (32 weeks from randomization), there will be up to 8-week additional follow-up period, concluding with the 12 weeks post-last dose follow-up visit (Visit 12)         
	
Design Features	
 
• 32-week treatment period, randomised, double-blind, placebo-controlled, parallel group, multicentre study of mepolizumab in adolescent and adult subjects with severe HES receiving SoC therapy.
 
• The same regimen of HES therapy will be maintained throughout the 32-week study treatment period unless there is worsening of symptom(s) that requires an increase in therapy. A reduction in dose for safety reasons, with return to the original dosing regimen if possible, is permitted in consultation with the GSK Medical Monitor.
 
• Subjects who withdraw from study treatment prematurely should continue in the study per protocol (including HES flare-related assessments) until 32 weeks from randomization.
 
• Investigators, participating subjects, and GSK study personnel will be blinded to absolute blood eosinophil counts, total white blood cell counts, and white blood count differentials (%) from randomization (Visit 2) until completing the 32-week period from randomization. Blood eosinophil-unblinded GSK personnel/delegates not involved with other aspects of study conduct will monitor the absolute blood eosinophil count results and trigger blinded OCS treatment to treat an eosinophilia when the blood eosinophil count reaches a pre-defined threshold (2 x baseline value or baseline value + 2500 cells/<math>\mu</math>L). Provided the subject's HES therapy has not been increased due to a symptom flare, the subject will take the blinded active OCS for ~2 weeks. A subject who does not reach the pre-defined blood eosinophilia threshold with a similar blood draw date will be selected to initiate blinded placebo OCS treatment, to maintain study blood eosinophil blinding. Approximately 2 weeks after the scheduled clinic visit, the blood eosinophil count will be assessed again for the subjects who
 

Overview of Study Design and Key Features	
	
started blinded OCS (both active and placebo). The subject who has taken active blinded OCS will be instructed to continue with a new course of blinded OCS until the next scheduled clinic visit if the blood eosinophil count is at or above the threshold unless the subject's HES therapy has been increased due to a symptom flare since the initiation of the current course of blinded OCS, and discontinue if the blood eosinophil count is below the threshold. For subjects taking placebo-blinded OCS, continuation/discontinuation of blinded OCS will be determined depending on the continuation/discontinuation of their matched subject on active-blinded OCS.
 
 
• An open-label study is also planned (study 205203) for subjects who complete study 200622.
 

Main subject entry criteria	
 
• Subjects <math>\geq 12</math> years with HES
 
• At least 2 HES flares within the past 12 months; at least one HES flare within the past 12 months must not be related to a decrease in HES therapy during the 4 weeks prior to the flare.
 
• Blood eosinophil count <math>\geq 1000</math> cells/<math>\mu\text{L}</math> during screening. Investigators were permitted to use local laboratory results to meet this inclusion criteria.
 

Dosing	
 
• 300 mg mepolizumab or placebo SC every 4 weeks (8 administrations) while continuing their HES therapy.
 
• The final dose of study treatment will be administered at Visit 10 (Week 28) with completion of the study treatment period achieved at the next 4-weekly visit.
 

Treatment Assignment	
 
• Subjects will be randomised in a 1:1 ratio to receive either mepolizumab or placebo in addition to SoC therapy.
 
• An initial sample size of N=80 subjects will be randomised. The proportion of subjects that have a HES flare will be monitored, blinded to treatment, and the total number of subjects randomised may be increased up to a maximum of 120 subjects if the blinded overall flare rate is predicted to be <math><30\%</math>. The blinded overall proportion of subjects who have a HES flare will be calculated based on the HES flare data available in the CRF. This will include all HES flares meeting flare endpoint definition 'a)' in Section 7.1.1. In order to maintain the blood eosinophil blinding, HES flares meeting flare end point definition 'b)' in Section 7.1.1 will not be included in the calculation of the blinded overall proportion.
 
• Treatments will be assigned randomly via an interactive response system (IRS).
 
• Randomization schedule will be generated using GSK validated randomisation software RandAll NG.
 
• Randomization stratified by region.
 

Time and events	
 
• See Appendix 2: Schedule of Activities.
 

Interim	
 
• An external Independent Data Monitoring Committee (IDMC) will
 

Overview of Study Design and Key Features	
Analysis	periodically review unblinded safety data from the study, in accordance with the IDMC Charter. The safety data analyses for the IDMC reviews will be performed by an independent statistical analysis data centre (SDAC). There are no circumstances under which IDMC review of the data would lead to a recommendation to stop for efficacy. Therefore, no adjustment to the final alpha level for efficacy will be made based on the safety stopping guidelines.

### 2.3. Statistical Hypotheses / Statistical Analyses

The primary efficacy endpoint is the proportion of subjects who experience a HES flare during the 32-week study treatment period. This study is designed to test the superiority of mepolizumab versus placebo. The primary analysis will test the following hypothesis:

- **Null hypothesis:** no difference between mepolizumab relative to placebo for the proportion of subjects who experience a HES flare during the 32-week study treatment period.
- **Alternative hypothesis:** the proportion of subjects who experience a HES flare during the 32-week study treatment period is smaller for mepolizumab compared to placebo.

Significance tests will be performed at the two-sided 5% level (one sided 2.5%).

### 2.4. Changes to the Protocol Defined Statistical Analysis Plan

- The following changes to the exploratory endpoints were made in this RAP:

Protocol Endpoint	RAP Endpoint	Rationale for Change
Proportion of subjects who receive blinded active OCS due to an elevated blood eosinophil level that meets the pre-defined threshold during the 32-week study treatment period	Proportion of subjects who have an elevated blood eosinophil level that meets the pre-defined threshold during the 32-week study treatment period	RAP endpoint considered to be more clinically meaningful as it includes all subjects with blood eosinophil counts meeting the pre-defined threshold during the 32-week study treatment period rather than including only the subset of these subjects who receive blinded active OCS. Subjects did not receive blinded active OCS if their physician had already increased their HES therapy based on symptoms.
Change from baseline in the BFI total and domain scores at Week 32	Change from baseline in the BFI total score at Week 32.	The BFI is a single construct and therefore domain scores are not applicable.
Proportion of subjects with a favourable response as measured by clinician- and subject-	Clinician- and subject-rated overall response to therapy score (RTS) at Week 32	Improvement/worsening is measured on a 7-point scale from significant worsening to significant improvement. The endpoint will be summarised and analysed as a 7-point ordinal endpoint to avoid loss of information and increase the sensitivity of the analysis.

Protocol Endpoint	RAP Endpoint	Rationale for Change
rated overall response to therapy score (RTS) at Week 32		
Serum free and total IL-5	Total IL-5	Free IL-5 levels are generally very low in serum (<BLQ) and are expected to decrease post dosing because most of the free IL-5 becomes complexed with mepolizumab. Hence only total IL-5 will be measured.

- Since some participants were randomised early in error prior to the first dose of mepolizumab, the following changes to the secondary endpoint derivations in the protocol are planned:
  - Time to first HES flare will be calculated from the date of first dose of study treatment and the onset date of the HES flare, rather than the date of randomisation and the onset date of the HES flare.
  - The rate of HES flares will be calculated using the date of the first dose of study treatment and the Week 32 visit/study withdrawal date, rather than the randomisation date and the Week 32 visit/study withdrawal date.
  - For the calculation of the change from baseline in BFI item 3, the mean of the 7 daily assessments of BFI item 3 up to but not including the date of first dose of study treatment will be used as the baseline assessment. Since BFI item 3 is measured daily after 6pm, the date of dosing will not be included in the calculation of the baseline BFI.

### **3. PLANNED ANALYSES**

#### **3.1. Interim Analyses**

An external Independent Data Monitoring Committee (IDMC) will periodically review unblinded safety data from the study, in accordance with the IDMC Charter. The safety data analyses for the IDMC reviews will be performed by an independent statistical analysis data centre (SDAC). There are no circumstances under which IDMC review of the data would lead to a recommendation to stop for efficacy of mepolizumab. Other than the emergency unblinding procedures described in Section 6.3 of the protocol, all personnel having direct responsibility for the conduct of the study will remain blinded to treatment groups for all data until the database is frozen.

#### **3.2. Final Analyses**

The final planned primary analyses will be performed after the completion of the following sequential steps:

1. All subjects have completed the study as defined in the protocol.
2. All required database cleaning activities have been completed and final database release (DBR) and database freeze (DBF) has been declared by Data Management.
3. A review has taken place by the unblinded global study manager to identify any subjects with a discrepancy between randomised treatment and actual treatment received. This information will be included in the SDTM dataset at DBF. Actual treatment arm will be derived within the ADaM datasets based on the treatment received for more than 50% of treatment administrations. If a subject received an equal number of both treatments then the actual treatment arm will reflect the treatment to which they were randomised.
4. All criteria for unblinding the randomisation codes have been met, and treatment allocations have been unblinded via the RandAll NG system, as described in SOP\_54840.

#### 4. ANALYSIS POPULATIONS

Population	Definition / Criteria	Analyses Evaluated
Screened	
 
All participants who were screened for eligibility i.e. for whom record exists in the database.
 
	
 
Study Population (Pre-screen and screen failures)
 

Enrolled	
 
All participants who were successfully screened and entered the study.
 
Note: screening failures (who never passed screening even if rescreened) and participants who were successfully screened but did not complete any visit 2 assessments are excluded.
 
	
 
Study Population (EudraCT required displays)
 

Intent-To-Treat (ITT)	
 
All randomised subjects
 
This population will be based on the treatment to which the subject was randomised.
 
Any subject who receives a treatment randomisation number will be considered to have been randomised.
 
	
 
Study Population
 
Efficacy
 
Listing of Planned and Actual Treatments
 

Per-Protocol (PP)	
 
Comprise all subjects in the ITT population not identified as full protocol deviators with respect to criteria that are considered to impact the primary efficacy analysis.
 
The decision to exclude a subject from the PP population or exclude part of their data from the PP population will be made prior to breaking the blind.
 
Protocol deviations that would exclude subjects from the PP population are defined in Appendix 1: Protocol Deviation Management and Definitions for Per Protocol Population.
 
	
 
Supplementary analysis of primary endpoint
 

Safety	
 
All subjects who are randomised and who receive at least one dose of study treatment. Randomised subjects will be assumed to have received study treatment unless definitive evidence to the contrary exists.
 
This population will be based on the treatment the subject actually received.
 
Subjects will be analysed according to treatment received for more than 50% of their treatment administrations. If a subject received an equal number of both treatments then they will be assigned to the treatment to which they were randomised.
 
	
 
Study Population
 
Safety
 

Pharmacokinetic	
 
All subjects in the ITT population who received
 
	
 
PK
 

Population	Definition / Criteria	Analyses Evaluated
	at least one dose of study treatment and for whom at least one PK sample was obtained, analysed and was measurable.	
Pharmacodynamic	
 
• All subjects in the ITT population who received at least one dose of study treatment and who also had a baseline PD measurement and at least one post-treatment PD measurement.
 
	
 
• PD
 

Refer to [Appendix 10](#): List of Data Displays which details the population used for each display.

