
This dose should also be able to prevent bursts of blood eosinophils, which are triggered by external factors not very well understood and/or following OCS reduction as part of SoC in clinical practice, and subsequently prevent flare.

The selection of the 4-week dosing interval is supported by mepolizumab half-life of approximately three weeks, the dose response meta-analysis, also based on a dosing interval of every four weeks, and the consistent maintenance of pharmacological effect over this 4-week dosing interval at doses of mepolizumab 75 mg IV/100 mg SC and higher (MEA112997) [[Pavord, 2012](#)].

Mepolizumab has been studied in patients with HES at doses three-fold higher than proposed in this study for durations of up to 11 years. During this time no apparent safety signal has been detected and no clinically meaningful trends in hematology or clinical chemistry have been noted. Data from mepolizumab treatment over a 10-fold

range (75 to 750 mg IV every 4 weeks) in patients with severe asthma also have not shown any apparent increase in adverse events or laboratory abnormalities and hence an absence of response and dose-response to increasing doses of mepolizumab. Of note a 300 mg SC mepolizumab dose is currently under investigation in an ongoing randomized, placebo-controlled study in patients with EGPA (MEA115921), a disease which shares many similarities with HES with regards to blood eosinophil levels at the time of diagnosis and also multi-organ involvement. Therefore, in addition to this placebo-controlled study assessing 300 mg SC dose of mepolizumab for the treatment duration of 32 weeks, Study MEA115921 will provide one-year safety data at 300 mg SC that may also be concomitantly administered with immunosuppressive therapies.

Taken together, the above information suggests a mepolizumab dose of 300 mg SC (delivered 3x100mg SC injections) every four weeks could provide clinical benefit in the HES patient population targeted in the HES Study 200622, and has therefore been selected for investigation for a treatment duration of 32 weeks.

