9. STATISTICAL CONSIDERATIONS AND DATA ANALYSES

9.1. Hypotheses

The primary efficacy endpoint is the proportion of subjects who experience an HES flare during the 32-week study treatment period. This study is designed to test the superiority of mepolizumab versus placebo. The primary analysis will test the following hypothesis:

- **Null hypothesis:** no difference between mepolizumab relative to placebo for the proportion of subjects who experience an HES flare during the 32-week study treatment period.
- **Alternative hypothesis:** the proportion of subjects who experience an HES flare during the 32-week study treatment period is smaller for mepolizumab compared to placebo.

Significance tests will be performed at the two-sided 5% level (one sided 2.5%).

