9.2. Sample Size Considerations

9.2.1. Sample Size Assumptions

This study is designed to test the superiority of mepolizumab versus placebo.

The primary efficacy endpoint is the proportion of subjects who experience an HES flare during the 32-week study treatment period. The power calculation assumes that 60% of subjects on placebo will experience an HES flare during the 32-week study treatment period. With a two-sided 5% level of significance and a sample size of 40 randomized subjects per arm, the null hypothesis will be rejected if the observed proportion of patients with an HES flare on placebo is 60% and on mepolizumab is 35% or less. If the true population proportion of subjects who would experience an HES flare during the 32-week study treatment period on placebo is 60% and on mepolizumab is 22%, the study has 90% power for demonstrating a statistically significant result for this assumed true population effect.

This endpoint is novel, and has not explicitly been used in clinical trials of HES. There is therefore little previous data on which to base estimates of the number of subjects who will experience an HES flare during the 32-week study treatment period.

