#### 16.1.1. Exclusions from Per Protocol Population

A subject meeting any of the following criteria will be excluded from the Per Protocol population:

Number	Exclusion Description
01	Inclusion #3 – Insufficient evidence that subject has been diagnosed with HES for at least 6 months at randomization (Visit 2).
02	Inclusion #4 – Subject did not have a history of two or more flares within the past 12 months prior to screening (Visit 1), with at least one HES flare not related to a decrease in HES therapy during the 4 weeks prior to the flare.
03	Inclusion #5 – Subject did not have a blood eosinophil count $\geq 1000$ cells/ $\mu\text{L}$ collected during screening (within 4 weeks prior to randomization). Investigators were permitted to use local laboratory results to meet this inclusion criteria, therefore if the screening central laboratory blood eosinophil count is $< 1000$ cells/ $\mu\text{L}$ but a local laboratory blood eosinophil count $\geq 1000$ cells/ $\mu\text{L}$ is available during screening the subject will not be considered a protocol deviation or excluded from the Per Protocol population.
04	Inclusion #6 – Subject was not on a stable dose of HES therapy for the 4 weeks prior to randomization (Visit 2).
05	Incorrect study treatment administered at any point during the study i.e. subject received placebo instead of mepolizumab or vice versa.
06	Subject received a medication or herbal remedy which may alter the course of HES or interact with the study treatment with the exception of HES therapy to treat a HES flare.

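### Subjects given both products in error can be tabulated as placebo in the safety and antibody tables despite real mepolizumab exposure

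*SAP*

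**What the plan says.** SAP Section 4 bases the Safety population on the treatment actually received, and gives two rules for subjects who received both products. The main rule goes by majority: "Subjects will be analysed according to treatment received for more than 50% of their treatment administrations". A separate rule covers an exact tie, and here the SAP falls back on randomisation: "If a subject received an equal number of both treatments then they will be assigned to the treatment to which they were randomised".

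SAP Section 3.2, step 3, builds the same rule into the analysis data sets. The actual treatment arm is "based on the treatment received for more than 50% of treatment administrations", again with ties to the randomised arm. Both SAP versions carry these rules.

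The Protocol (Section 9.3.1) requires only one dose for entry to the Safety population and gives no rule for assigning the arm.

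The per-protocol set is stricter. SAP Section 16.1.1, criterion 05, excludes a subject for "Incorrect study treatment administered at any point during the study i.e. subject received placebo instead of mepolizumab or vice versa". That exclusion reaches only the supplementary efficacy analysis.

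**The concern.** A majority rule is a weak measure of exposure when one product is a long-acting antibody and the other is 0.9% saline (Protocol 6.1). Protocol 7.4 describes systemic reactions as usually starting within hours of an injection, so one dose is enough. Exposure also lasts: the four-week interval is "supported by mepolizumab half-life of approximately three weeks". The on-treatment window for adverse events (SAP 16.4.4) runs from the first to the last dose of study treatment plus 28 days, whichever product was given, so an event after a mepolizumab dose goes to whichever column the majority rule selects.

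The displays at stake use the Safety population: the adverse-event tables, the special-interest relative risks (SAP 11.1.1, Table 4.26, Figure 4.2), adverse events by antibody result (Table 4.10) and the antibody tables 4.60 to 4.62. A reactor or antibody-positive subject placed under placebo raises the placebo rate and lowers the mepolizumab-to-placebo relative risk. The SAP plans no any-exposure display and no sensitivity analysis for mixed exposure.

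**Working it through.** **Inputs.** Eight planned administrations per subject (Protocol 6.2, SAP 2.2); the majority and tie rules (SAP 4 and 3.2); 40 subjects per arm (Protocol 9.2.1); half-life of about three weeks (Protocol 4.5).

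**The plan's own figure.** The only design figure is for efficacy: "on placebo is 60% and on mepolizumab is 22%, the study has 90% power", at 40 per arm and two-sided 5%. With d = 0.60 − 0.22 = 0.38 and mean proportion 0.41:

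- SE under the null = √(0.41 × 0.59 × 2/40) = 0.1100.
- SE under the alternative = √((0.60 × 0.40 + 0.22 × 0.78)/40) = 0.1014.
- Continuity-corrected z = (0.38 − 0.025 − 1.96 × 0.1100)/0.1014 = 1.37, so power is 91.5%. Exact Fisher power is 91.9%. Without correction it is 94.8%.

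The stated 90% is reproduced within two points. This point needs only the 40 per arm.

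**Step 1: apply the rule to every mixed pattern.** Let m be the number of mepolizumab administrations out of 8, the rest being placebo.

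| Randomised to | Tabulated as placebo | Tabulated as mepolizumab |
|---|---|---|
| Placebo | m = 1, 2, 3, 4 | m = 5, 6, 7 |
| Mepolizumab | m = 1, 2, 3 | m = 4, 5, 6, 7 |

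So 4 + 3 = 7 of 14 patterns go to placebo and 3 + 4 = 7 to mepolizumab. Over all totals from 2 to 8 administrations, 32 patterns have mepolizumab at no more than half. Of these, 28 go to placebo. The other 4 are exact ties in subjects randomised to mepolizumab.

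**Step 2: a short course.** A subject randomised to placebo receives mepolizumab at Visit 2 in error, has a systemic reaction, receives placebo at Visit 4 and stops. That is 1 of 2, a tie, so both subject and reaction are tabulated as placebo.

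**Step 3: carry-over.** With simple exponential decline at a three-week half-life, the fraction left one dosing interval (4 weeks) after a dose is 0.5^(4/3) = 0.40. Saline leaves nothing.

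**Step 4: size.** One subject is 1/40 = 2.5 percentage points of an arm. A purely hypothetical relative risk can be built from the local injection-site reaction rates that Protocol 4.6.1 quotes from severe asthma studies: 8% v 3%, or 3.2 v 1.2 expected events at 40 per arm, taken as 3 v 1. Add one placebo-randomised subject with minority mepolizumab exposure who reacts to it. With SE(log RR) = √(1/a − 1/n₁ + 1/b − 1/n₂):

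- Majority rule: (3/40)/(2/40) = 1.50; SE = √(1/3 − 1/40 + 1/2 − 1/40) = 0.885; 95% interval 0.26 to 8.5.
- Any-mepolizumab rule: (4/41)/(1/39) = 3.80; SE = √(1/4 − 1/41 + 1 − 1/39) = 1.095; 95% interval 0.44 to 32.6.

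The intervals are very wide and overlap almost entirely.

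**Step 5: the alternative rule.** If any mepolizumab dose places the subject under mepolizumab, 0 of the 14 mixed patterns go to placebo.

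**The case against.** The strongest reply is that majority-received is one legitimate reading of treatment actually received, was prespecified identically in both SAP versions and contradicts nothing in the Protocol. It is numerically even-handed, with 7 of 14 mixed patterns going each way. The alternative misattributes too: one wrong dose in eight would carry about seven placebo intervals of events, laboratory values and ECGs into the mepolizumab column. An any-exposure display added as support would answer the point without replacing the main rule.

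Most of this stands. What it does not meet is the asymmetry of consequence. Placebo time counted under mepolizumab adds background events to the drug. Mepolizumab time counted under placebo assigns drug reactions and antibodies to saline, which cannot cause them pharmacologically.

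A reader might go further and infer that the rule hides harm. The documents do not support that. Mis-dosed subjects would be visible in the listings of planned and actual treatment (Listing 5) and of exposure (Listing 13), in the summaries of important deviations and per-protocol exclusions, in the reaction listings that show the number of prior doses (Listings 35 to 38), and for antibodies in Listing 50. The Protocol (4.6.1) also promises a review of adverse events in antibody-positive subjects after unblinding. These displays disclose the cases; they do not correct a table.

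Nor do the documents show that mis-dosing occurred or was expected. The discrepancy review, criterion 05 and Listing 5 are contingency provisions. Where the SAP knows of a conduct problem it says so (early randomisation in 2.4, a site investigation in 7.1.4.1), and it reports no wrong-product administration. Error is possible, because unblinded site staff prepare open-label vials and the site supplies the saline (Protocol 6.1 and 6.2), but that is all that can be said.

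**Conclusion.** The point holds in a narrow form. Among subjects who received both products, those with mepolizumab at fewer than half of their own administrations, or at exactly half if randomised to placebo, are tabulated as placebo. Events and antibodies after real mepolizumab exposure then fall in the placebo column.

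Two broader readings are tempting and wrong. First, not everyone at half or below is moved: a tie in a subject randomised to mepolizumab stays under mepolizumab. Second, a subject who stops after a few mepolizumab doses and never receives placebo is not moved, because the denominator is that subject's own administrations.

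The size cannot be computed, because the documents give no number of mis-dosed subjects. With none, nothing changes. With 40 per arm, each affected subject is 2.5 percentage points of an arm. The contrast of 1.5 with 3.8 assumes both a mis-dosing and a reaction, neither documented, and borrows local-reaction rates from asthma; for systemic reactions Protocol 4.6.1 calls the rates similar. It shows how sensitive a relative risk is at these counts and supports no conclusion about the drug.

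This is a cheap improvement to a contingency rule. It is not a flaw that threatens the safety conclusions.

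**What to change.** In SAP 3.2 step 3 and Section 4, replace the majority and tie rules with wording such as: *For the Safety population and all safety and immunogenicity displays, a subject who received at least one administration of mepolizumab is analysed in the mepolizumab group. All mixed-exposure subjects are listed with the date of each product given, so that events before the first mepolizumab dose can be identified.* Leave ITT efficacy as randomised.

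The change should be made before the database is frozen and the treatment codes are released, since a later change would look data-driven.

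The cost is two sentences and one flag in the analysis data set; Listings 5 and 13 already cover much of the listing. The downside is that events in a mixed-exposure subject's placebo-only time also move to the mepolizumab column. That is the cautious direction for safety, and the dated listing lets a reader separate events that preceded any mepolizumab.
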